4.7.3 Additional safety assessments

4.7.3.1 Laboratory variables, vital signs and electrocardiograms (ECGs)

The following laboratory variables, vital signs and electrocardiogram (ECG) variables will be analyzed. They will be converted into standard international units.

- Hematology:
 - Red blood cells and platelets and coagulation: hemoglobin, hematocrit, red blood cell count, platelet count

- White blood cells: white blood cell count, neutrophils, lymphocytes, monocytes, basophils, eosinophils
- Clinical chemistry:
 - Metabolism: glucose, total cholesterol, total protein, creatine phosphokinase
 - Electrolytes: sodium, potassium, chloride, bicarbonate
 - Renal function: creatinine, blood urea nitrogen, uric acid
 - Liver function: alanine aminotransferase, aspartate aminotransferase, alkaline phosphatase, lactate dehydrogenase, total bilirubin, albumin
 - Pregnancy test: Serum β -human chorionic gonadotropin (all female participants) will be performed at screening (V1) in women of childbearing potential, and a urine pregnancy test will be performed at V2 and every 4 weeks thereafter.
 - Hepatitis screen: hepatitis B surface antigen (HBs Ag), hepatitis B surface antibody (HBs Ab), hepatitis B core antibody (HBc Ab), hepatitis C virus antibodies (HCV Ab) will be tested at screening (V1). In case of results showing HBs Ag (negative) and HBc Ab (positive), an hepatitis B virus (HBV) deoxyribonucleic acid (DNA) testing will be performed and should be confirmed negative prior to randomization. In case of results showing HCV Ab (positive), an HCV ribonucleic acid (RNA) testing will be performed and should be confirmed negative prior to randomization.
 - HIV screen: Anti-HIV-1 and HIV-2 antibodies will be tested at Visit 1.
 - TB test (performed locally if required and results noted in the eCRF).
- Urinalysis:
 - Urinalysis will include specific gravity, pH, glucose, ketones, blood, protein, nitrate, leukocyte esterase, urobilinogen and bilirubin. If positive for protein and/or red blood cells, microscopic analysis will be performed by the central laboratory. Creatinine, leukotriene and tetrnor PGDM will be tested by the central laboratory.
- Vital signs: pulse rate (beats per minute), systolic and diastolic blood pressure (mmHg) in a semi-supine or sitting position after 5 minutes, weight, respiratory rate (breaths per minute), temperature (degrees Celsius) and height (screening only).
- ECG variables: heart rate, PR, QRS, QT, and QTcF intervals after 10 minutes of rest in the supine position. Data are locally collected and read at screening (V1) and Week 24 (V6).

Data below the lower limit of quantitation/detection limit (LLOQ) will be replaced by half of the LLOQ, data above the upper limit of quantification will be replaced by ULOQ value.

Quantitative analyses

For all laboratory variables, vital signs and ECG variables above, descriptive statistics for results and changes from baseline will be provided for each analysis window, the last value and the worst value during the on-treatment period. These analyses will be performed using central measurements only (when available) for laboratory variables.

For all parameters, mean changes from baseline with the corresponding standard error will be plotted over time.

Analyses according to PCSA

Analysis of potentially clinically significant abnormality (PCSA) will be performed based on the PCSA list in effect at Sanofi at the time of the database lock. For parameters for which no PCSA criteria are defined, similar analyses will be done using the normal range, if applicable.

Analyses according to PCSA will be performed based on the worst value during the treatment-emergent period, using all measurements (either local or central, either scheduled, nonscheduled or repeated).

For laboratory variables, vital signs and ECG variables above, the incidence of participants with at least one PCSA during the treatment-emergent period will be summarized regardless of the baseline level and according to the following baseline status categories:

- Normal/missing
- Abnormal according to PCSA criterion or criteria;

Additional analyses for suspect drug-induced liver injury

The following additional analyses will be performed for drug-induced liver injury:

- Time to onset of the initial ALT or aspartate aminotransferase (AST) elevation ($>3 \times \text{ULN}$) and total bilirubin elevation ($>2 \times \text{ULN}$) during the treatment-emergent period will be analyzed using Kaplan-Meier method.
- A graph of the distribution of peak values of ALT versus peak values of total bilirubin during the treatment-emergent period will be provided.
- For each liver function test (eg, ALT), participants having a PCSA (eg, ALT $>5 \text{ ULN}$) will be summarized using the following categories: Returned to baseline PCSA status (or returned to value $\leq \text{ULN}$ in case of missing baseline) before last IMP dose, Returned to baseline PCSA status after last IMP dose, Never returned to baseline PCSA status, No assessment after elevation. This summary will be performed by categories of elevation (ALT $>3, >5, >10, >20 \text{ ULN}$).

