1.3 SCHEDULE OF ACTIVITIES (SOA)

Procedure	Screening (2 to 4 weeks before Day 1)	Intervention period (Weeks)					Follow-up (12 weeks)	Notes
		0 (Day 1)	4	8	12	24		
Visit	1	2 ^a	3	4	5	6 ^b (EOT)	7 (EOS)	Visit window: ± 3 days for Visits 3, 4, 5, 6, and 7.
Screening and baseline								
Informed consent	X							Separate consent to be obtained for optional procedures (skin biopsy, DNA and RNA sampling, serum/plasma sampling for archival, and photography; HIV test if specific consent locally required).
Medical history	X							
Prior and concomitant medication	X	X	X	X	X	X	X	Concomitant medication will be collected throughout the study.
Demography	X							
Inclusion and exclusion criteria	X	X						
Hepatitis ^c , HIV serology, TB test	X							HBs Ag, HBs Ab, HBc Ab, HCV Ab, HIV screen (Anti-HIV-1 and HIV-2 antibodies), TB test (performed locally if required and results noted in the eCRF).
Randomization		X						
Study intervention^d								
Dispense or download e-diary	X	X	X	X	X	X	X	Device will be dispensed at Screening (including instructions for use). At EOS, the e-diary will be downloaded and returned to the site.
Participant e-diary training	X	X						
Call IVRS/IWRS	X	X	X	X	X	X	X	At screening visit, IVRS/IWRS will be called after medical history check.
IMP administration		X	X	X	X			IMP administration Q2W (± 3 days) from Week 0 until Week 22. Between visits, the participants will self-inject IMP at home or may choose to have injections administered at home by a caregiver or at the study site.

Procedure	Screening (2 to 4 weeks before Day 1)	Intervention period (Weeks)					Follow-up (12 weeks)	Notes
		0 (Day 1)	4	8	12	24		
Visit	1	2 ^a	3	4	5	6 ^b (EOT)	7 (EOS)	Visit window: \pm 3 days for Visits 3, 4, 5, 6, and 7.
Safety^d								
Physical examination	X	X				X	X	Including skin (full body skin exam), nasal cavities, eyes, ears, respiratory, cardiovascular, gastrointestinal, neurological, lymphatic, and musculoskeletal systems.
Vital signs	X	X	X	X	X	X	X	Including SBP and DBP (mmHg), pulse rate (beats per minute), body temperature (°C), and respiratory rate. Body weight will be recorded at Visits 1, 6, and 7 only. Height will be recorded at Visit 1 only.
12-lead ECG	X					X		Locally collected and read.

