6.1 STUDY INTERVENTION(S) ADMINISTERED

Table 2 - Overview of study interventions administered

ARM name	Dupilumab	Placebo
Intervention name	Dupilumab 300 mg	Placebo matching dupilumab 300 mg
Type	Biological/Vaccine	Other
Dose formulation	A 150 mg/mL dupilumab solution in a pre-filled syringe to deliver 300 mg in 2 mL	Identical formulation to the active 300 mg formulation without dupilumab, in a pre-filled syringe to deliver placebo in 2 mL
Unit dose strength(s)	300 mg	0 mg (placebo)
Dosage level(s)	300 mg every 14 ±3 days after an initial loading dose of 600 mg	0 mg every 14 ±3 days with a loading dose of 0 mg
Route of administration	Subcutaneous ^a	Subcutaneous ^a
IMP and NIMP	IMP	IMP
Packaging and labeling	One glass pre-filled syringe packed in a patient kit box. Both the glass pre-filled syringe and the box will be labeled as required per country requirement.	One glass pre-filled syringe packed in a patient kit box. Both glass pre-filled the syringe and the box will be labeled as required per country requirement

^a Subcutaneous injection sites should alternate between the upper thighs, 4 quadrants of the abdomen or the upper arms, so that the same site is not injected twice during consecutive administrations. Injection in the upper arms can only be done by a trained person (parent/legally authorized representative/caregiver trained by Investigator or Delegate) or health care professional but not the participant themselves.

IMP: investigational medicinal product; NIMP: noninvestigational medicinal product.

The Investigator or delegate will train the patient (or caregiver) how to prepare and inject IMP at Visit 2. He/she will inject the first of the two injections. The participant (or caregiver) will perform the second injection under the supervision of the Investigator or delegate. Patient should also be trained by the site staff to recognize potential signs and symptoms of hypersensitivity reaction in order to self-monitor at home for at least 30 minutes (or longer per country specific or local site-specific requirements) following injection. In case of hypersensitivity symptoms the patient should contact healthcare provider/emergency. The training must be documented in the participant's study file.

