4 STATISTICAL ANALYSES

4.1 GENERAL CONSIDERATIONS

In general, continuous data will be summarized using the number of observations available, mean, standard deviation (SD), median, minimum, and maximum. Categorical and ordinal data will be summarized using the count and percentage of participants.

The baseline value of efficacy parameters is defined as the last available value before randomization and prior to the first dose of study medication unless below eDiary data (WI-NRS, skin Pain-NRS and Sleep-NRS) score or otherwise specified.

The baseline for weekly average WI-NRS (skin Pain-NRS and Sleep-NRS) score is defined as the average of daily non-missing scores obtained during the 7 days prior to randomization.

The baseline value of the other parameters is defined as the last available value prior to the first dose of investigational medicinal product (IMP) if the participant is treated, or the last available value up to randomization if the participant is not exposed to IMP.

Observation period

The observation period will be divided into 4 segments:

- The **pre-treatment period** is defined as the period up to first IMP administration.
- The **treatment-emergent (TE) period** is defined as the period from the first IMP administration to the last IMP administration + 98 days. The treatment-emergent period includes the following 2 periods:
 - The **on-treatment period** is defined as the period from the first IMP administration to the last administration of the IMP + 14 days
 - The **residual treatment period** is defined as the period from the end of the on-treatment period to the end of the treatment-emergent period.
- The **post-treatment period** is defined as the period from the end of the treatment-emergent period.

The on-study observation period is defined as the time from start of intervention until the end of the study defined as the status date collected on e-CRF page “Completion of End of Study”.

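### SAP 4.1 ends the on-treatment period 14 days after the last dose with no room for the ±3-day windows, so some on-schedule Week 24 labs, vital signs and ECGs drop out of the last-value and worst-value summaries

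*SAP*

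**What the plan says.** SAP 4.7.3.1, under quantitative analyses, requires descriptive statistics for results and changes from baseline "for each analysis window, the last value and the worst value during the on-treatment period". SAP 4.1 says that the on-treatment period "is defined as the period from the first IMP administration to the last administration of the IMP + 14 days". The longer treatment-emergent period is "defined as the period from the first IMP administration to the last IMP administration + 98 days".

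Protocol 1.3 sets "IMP administration Q2W (± 3 days) from Week 0 until Week 22" and gives "Visit window: ± 3 days for Visits 3, 4, 5, 6, and 7"; Visit 6 is the Week 24 end-of-treatment visit. SAP Table 10 puts Week 22 at Day 155 and Week 24 at Day 169. Table 12 also targets Day 169 for Visit 6.

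Labs and vital signs are scheduled at Weeks 4, 8, 12 and 24 during treatment, with nothing between Weeks 12 and 24. ECGs are scheduled only at screening and Week 24.

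Table 12 assigns safety values to visits by study day and states no on-treatment condition. For Visit 6 it accepts Days 127-210 for vital signs, hematology and biochemistry, any day after 126 for urinalysis, and any post-dose day for ECG. The PCSA analyses, and the liver time-to-onset and peak-value analyses, use the treatment-emergent period.

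**The concern.** The cut-off equals the nominal dose-to-visit interval, so it has no slack. If the Week 22 injection is a day early, or the visit a day late, and the other does not offset it, every Week 24 result falls outside the on-treatment period although the participant followed the protocol throughout.

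For that participant the last scheduled on-treatment lab or vital sign reverts to Week 12, half-way through treatment, and the worst value is taken over Weeks 4 to 12. For ECG nothing scheduled is left. The last and worst rows would then mix participants followed to Week 24 with participants followed to Week 12, according to which permitted day was booked. Their denominators could differ from the Week 24 row in the same output with no stated reason.

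Other parts of the SAP treat Week 24 as belonging to treatment. Section 4.8.1 lists the Week 24/EOT sample with the trough concentrations and calls only Week 36 post-treatment. Section 4.7.1 has an exposure category for 24 weeks plus up to 3 days. The dosing window was therefore foreseen for exposure but not for this cut-off.

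**Working it through.** **Inputs.** Last planned dose Day 155 ± 3 and Week 24 visit Day 169 ± 3 (Protocol 1.3; SAP Tables 10 and 12). On-treatment end: last dose + 14 days (SAP 4.1). Dropout 15% of about 150 randomized (Protocol 9.2), used only for a head count. The spread of actual days inside the windows is not given, so it is assumed below.

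**The plan's own figure.** 169 − 155 = 14 days, equal to the cut-off.

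**Permitted gap.**
- Shortest: (169 − 3) − (155 + 3) = 8 days.
- Longest: (169 + 3) − (155 − 3) = 20 days.

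Counting day 14 as inside the period, visits on days 15 to 20 are on schedule but excluded.

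**Share excluded.** Let the dose and visit offsets be independent with the same distribution on −3 to +3. Then P(gap > 14) = (1 − P(gap = 14)) / 2, which is always below 50%. If a fraction q falls on the exact day and the rest is spread evenly over the other six days, P(gap = 14) = q² + (1 − q)²/6.

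| Assumed timing | P(gap = 14) | Share excluded |
|---|---|---|
| Uniform over ±3 days | 7/49 = 0.143 | 21/49 = 42.9% |
| 50% on exact day | 0.25 + 0.25/6 = 0.292 | 35.4% |
| 70% on exact day | 0.49 + 0.09/6 = 0.505 | 24.8% |
| 80% on exact day | 0.64 + 0.04/6 = 0.647 | 17.7% |
| 90% on exact day | 0.81 + 0.01/6 = 0.812 | 9.4% |
| Visit always 14 days after actual dose | 1 | 0% |

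Skewed timing moves the share either way:
- Visits uniform on 0 to +3 with exact doses: 3/4 = 75%.
- Visits uniform on 0 to +3 with doses uniform on −3 to 0: 15/16 = 93.8%.
- Visits uniform on −3 to 0 with doses uniform over ±3: 6/28 = 21.4%.

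**Head count.** 150 × 0.85 = 127.5 completers over both arms. At 9.4% that is about 12 people, at 17.7% about 23, and at 42.9% about 55.

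**After the change.** With the end at last dose + 20 days (14 + 3 + 3), no completer dosed and seen within the scheduled windows is excluded.

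**Alternative reading of the dosing window.** Protocol Table 2 words the regimen as "300 mg every 14 ±3 days after an initial loading dose of 600 mg". If the ±3 days run from the previous dose rather than the scheduled day, early dosing could accumulate over the five intervals from Week 12 to Week 22. The longest gap would then be 14 + 5 × 3 + 3 = 32 days, and 20 days would not cover every case.

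**The case against.** The strongest reply is that the Week 24 data are analysed elsewhere, and this is correct. The by-window Week 24 row, not the last-value row, is the direct summary of 24 weeks of dosing, and Table 12 keeps the values there. The PCSA incidence tables, the time to ALT/AST and bilirubin elevation, and the peak ALT and bilirubin plot all run to last dose + 98 days. A reader might infer that abnormalities or the only post-baseline ECG vanish from the safety analysis; they do not. One could read the phrase in 4.7.3.1 as restricting the by-window rows to the on-treatment period too. But the Week 36 row (after Day 210) would then be empty for every on-schedule completer, whose on-treatment period ends by Day 158 + 14 = 172.

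A reader might also infer that some 35-43% of completers are affected. The documents do not support a figure. That range needs independent timing with no more than about half of doses and visits on the exact day.

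Nor do the documents show that participants who missed doses are wrongly dropped. Missing the Week 22 dose puts the nominal gap at 169 − 141 = 28 days, and missing three consecutive doses puts it at 42 days or more. Leaving out such values is what an on-treatment rule is meant to do. Protocol 7.1.1 asks for the early-termination visit as soon as possible, so some of those visits will fall within 14 days, and earlier on-treatment labs and vital signs still count.

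Fourteen days is also one dosing interval, used for exposure duration and for a concomitant-medication summary, and safety is descriptive without testing. That explains the number. It does not explain why a visit within the protocol's own window should count as off treatment.

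**Conclusion.** The defect stands, with limited scope. The 14-day cut-off ignores both ±3-day windows. An on-schedule completer seen 15 to 20 days after the last dose is left out of the last-value and worst-value rows for Week 24 labs and vital signs, and for the only scheduled post-baseline ECG.

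The existence of the gap follows from the documents' dates alone. Its size does not: about 9% to 43% under the independent, symmetric assumptions shown, 0% if visits are tied to the actual dose date, and higher if visits run late. The other safety summaries named above retain the data, so no safety conclusion depends on this. It is a cheap improvement.

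**What to change.** Add one sentence to SAP 4.7.3.1: for the last-value and worst-value quantitative summaries only, the on-treatment period runs from first IMP to last IMP + 20 days (14 + 3 + 3). Leave the Table 12 windows, PCSA, AE tables, exposure duration and the 98-day treatment-emergent period as they are.

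Do not extend the period to the later of that date and the Week 24/EOT visit. Protocol 7.1.1 asks early discontinuers to attend remaining visits, so such a clause would label values taken months after the last dose as on-treatment. With the fixed 20 days, a completer who missed the Week 22 dose stays excluded: the shortest in-window gap is 166 − 144 = 22 days. The sponsor should also confirm that the ±3-day dosing window is counted from the scheduled day, since the 20 days rest on that reading.

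Cost: one sentence and one date derivation before the primary database lock. The downside is that a few values up to 6 days beyond one dosing interval are labelled on-treatment.

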4.8 OTHER ANALYSES

4.8.1 Pharmacokinetic analyses

Predose dupilumab concentrations in serum at Visit 2 (Day 1), dupilumab trough concentrations at Week 4, Week 8, Week 12, Week 24/EOT Visit and post-treatment dupilumab concentrations at Week 36/EOS Visit will be provided.

Concentrations of dupilumab in serum will be summarized in the PK population using arithmetic and geometric means, SD, standard error of the mean (SEM), coefficient of variation (CV),

minimum, median and maximum per sampling time. If date and/or time of the drug injection and/or sampling is missing then the concentration will not be taken into account. For drug-treated participants, where concentration values are below the lower limit of quantification (LLOQ), one-half of the LLOQ will be used. Values will be expressed in the tables with no more than three significant figures. For participants in the placebo group, concentration values that are below the LLOQ will be taken into account with a plasma concentration considered equal to 0.

4.8.2 Immunogenicity analyses

Anti-drug antibody (ADA) status to dupilumab (negative or titer value, if positive in the ADA assay) at Visit 2 (Day 1), Week 12, Week 24/EOT and follow up at Week 36 will be provided. The neutralizing antibody status for ADA positive samples will be provided.

Incidence will be provided for the following ADA response categories:

Pre-existing immunoreactivity is defined as:

An ADA positive response in the assay at baseline with all post first dose ADA results negative, OR an ADA positive response at baseline with all post first dose ADA responses less than 4-fold over baseline titer levels.

Treatment-emergent ADA response is defined as:

A positive response in the ADA assay post first dose, when baseline results are negative or missing.

Treatment-emergent ADA responses are further classified as Persistent, Indeterminate or Transient

- A) Persistent Response- defined as a treatment-emergent ADA response with two or more consecutive ADA positive sampling time points, separated by greater than ($>$) 12-week period (84 days), with no ADA negative samples in between.
- B) Indeterminate Response- defined as a treatment-emergent response with only the last collected sample positive in the ADA assay
- C) Transient Response - defined as a treatment-emergent response that is not considered persistent OR indeterminate

Treatment-boosted response is defined as:

An ADA positive response in the assay post first dose that is greater-than or equal to 4-fold over baseline titer levels, when baseline results are positive.

Titer values (Titer value category)

- Low (Titer < 1000)
- Moderate ($1000 \leq \text{Titer} \leq 10\,000$)
- High ($\text{Titer} > 10\,000$)

The following summary will be provided based on ADA population:

- Number (%) of participants with pre-existing immunoreactivity
- Number (%) of participants with treatment-emergent ADA
- The summary statistics (including number, median, Q1, Q3, minimum and maximum) of the peak post-baseline titer for participants with treatment-emergent ADA, and participants with persistent, indeterminate and transient ADA response
- Number (%) of participant with transient treatment-emergent ADA
- Number (%) of participants with persistent treatment-emergent ADA
- Number (%) of participants with indeterminate treatment-emergent ADA
- Number (%) of participants with treatment-boosted ADA
- The summary statistics (including number, median, Q1, Q3, minimum and maximum) of the peak post-baseline titer for participants with treatment-boosted ADA
- The summary statistics (including number, mean, SD, median, Q1, Q3, minimum and maximum) of the ratio of peak post-baseline titer to baseline titer for participants with treatment-boosted ADA
- Listing of ADA peak titer levels and neutralizing antibody status
- Number (%) of participants with neutralizing antibody status.

Kinetics of treatment-emergent ADA response

Number (%) of participants with treatment-emergent ADA positive response at each visit will be summarized, including titer categories (lower, moderate, and high titer), by each intervention group.

A plot of percentage of participants with treatment-emergent ADA positive response at each visit will be provided by each intervention group.

Association of Immunogenicity with Exposure, Safety and Efficacy

The safety and efficacy analyses mentioned below will be conducted using the following categories:

- ADA positive participants: Participants with treatment-emergent or treatment-boosted response.
- ADA negative participants: Participants with pre-existing immunoreactivity or negative in the ADA assay at all time points.

Association of ADA with PK

Associations between ADA variables (eg, ADA peak titers, neutralizing antibody status, treatment-emergent, persistent, indeterminate and transient response, treatment-boosted) and concentration of dupilumab in serum may be explored for each dupilumab dose group. A plot of

concentration of functional dupilumab versus visit will be provided by ADA classifications for the dupilumab dose group. Individual participant plots of dupilumab concentration according to ADA status will be provided to assess the impact of ADA on PK.

Association of ADA with clinical efficacy endpoints

Associations between the ADA variables (eg, ADA peak titers, neutralizing antibody status, treatment-emergent, persistent and treatment-boosted) and the primary efficacy endpoint may be explored for the dupilumab dosed group.

Association of ADA with clinical safety endpoints

Association of safety versus ADA status may be analyzed in the ADA population. The safety assessment may focus on the following events:

- Severe injection site reactions last longer than 24 hours or serious injection site reactions
- Hypersensitivity reactions (SMQ (20000214) hypersensitivity narrow search confirmed by medical review)
- Anaphylactic reactions (SMQ (20000021) anaphylactic reaction narrow search)

Associations between ADA variables (eg, ADA peak titers, neutralizing antibody status, treatment-emergent, persistent and treatment-boosted) and safety may be explored.

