4.9 INTERIM ANALYSES

No interim analysis is planned.

A primary database lock will be performed when all randomized participants in this study have completed their 24-week treatment phase. Final analyses in the CSR will be based on this database.

The database will be updated at the end of the study for all participants to include the post-treatment follow-up information and updates for the events previously ongoing at the time of the primary lock. Additional data between this database lock and last participant completing last visit will be summarized in a CSR addendum.

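### Persistent ADA requires positives more than 84 days apart, but scheduled ADA samples are exactly 84 days apart (±3 days per visit), so visit timing rather than assay results can decide Persistent versus Transient

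*SAP*

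**What the plan says.** SAP 4.8.2 splits treatment-emergent ADA responses into three classes.

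- **Persistent:** "two or more consecutive ADA positive sampling time points, separated by greater than" a "12-week period (84 days), with no ADA negative samples in between".
- **Indeterminate:** the last collected sample is the only positive one.
- **Transient:** the remainder, "defined as a treatment-emergent response that is not considered persistent OR indeterminate".

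The same section reports ADA status "at Visit 2 (Day 1), Week 12, Week 24/EOT and follow up at Week 36 will be provided". The schedule in Protocol 1.3 agrees: ADA is sampled at Visits 2, 5, 6 and 7, with ±3 days allowed at each post-baseline visit. SAP 5.4, Table 13, gives target Days 85, 169 and 253 for Weeks 12, 24 and 36.

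Section 4.8.2 does not say whether separation is counted in nominal visit days or actual sampling dates. Nor does it say whether the span runs from first to last positive or between each adjacent pair.

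The classes feed committed outputs, including "Number (%) of participants with persistent treatment-emergent ADA", the matching transient count, and summaries of "peak post-baseline titer for participants with treatment-emergent ADA, and participants with persistent, indeterminate and transient ADA response".

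On timing, SAP 4.9 says "A primary database lock will be performed when all randomized participants in this study have completed their 24-week treatment phase" and "Final analyses in the CSR will be based on this database". It also provides for a database update at the end of the study and a CSR addendum.

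**The concern.** The threshold equals the sampling interval and must be strictly exceeded. The definition sets two positives as the minimum, yet two neighbouring scheduled positives sit exactly on the excluded boundary. Whether they count then depends on a convention that the SAP does not state or, on actual dates, on whether one visit was a day early or late within its permitted window.

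Because Transient is a residual class, the failure goes in a misleading direction. A participant positive at Weeks 24 and 36 with a gap of 84 days or less is labelled Transient although no negative sample followed.

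At stake is the meaning of the persistent and transient counts and of the titers by class. On nominal days every pair of adjacent positives goes to Transient. On actual dates, participants with the same positive/negative pattern can be split by scheduling alone.

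**Working it through.** **Inputs.** Threshold strictly more than 84 days (SAP 4.8.2); target Days 85, 169, 253 (SAP 5.4, Table 13); window ±3 days per visit (Protocol 1.3).

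**The plan's own figure.** 12 × 7 = 84 days, which reproduces the SAP's conversion.

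**Nominal gaps.** 169 − 85 = 84; 253 − 169 = 84; 253 − 85 = 168. Neither adjacent gap exceeds 84.

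**Classification on nominal days**, baseline negative, span from first to last positive in an unbroken run:

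| Weeks 12 / 24 / 36 | Rule >84 days | Rule ≥78 days |
|---|---|---|
| + + + | Persistent | Persistent |
| + + − | Transient | Persistent |
| − + + | Transient | Persistent |
| + − + | Transient | Transient |
| + − − | Transient | Transient |
| − + − | Transient | Transient |
| − − + | Indeterminate | Indeterminate |

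Two of the seven positive patterns change. If instead each adjacent pair had to exceed 84 days, even + + + would fail on nominal days.

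**Actual dates within the windows.** Gap = 84 + (offset at later visit) − (offset at earlier visit), each offset from −3 to +3.

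- Minimum 84 − 6 = 78; maximum 84 + 6 = 90.
- Of 7 × 7 = 49 offset pairs, 21 give more than 84 days, 7 give exactly 84 and 21 give fewer.
- Weeks 12 to 36: 168 ± 6, so 162 to 174 days, always above the threshold.

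**Share of adjacent in-window positives labelled persistent (assumed offsets).** The documents give no distribution of visit offsets. If offsets are independent and identically distributed, P(gap > 84) = (1 − P(tie)) / 2 by symmetry.

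- All visits on target: P(tie) = 1, share 0%.
- Half on target, the rest spread evenly over the other six days: P(tie) = 0.25 + 6 × (1/12)² = 0.292, share 35%.
- Uniform over seven days: P(tie) = 7/49 = 0.143, share 43% (21/49).

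Systematic lateness at the later visit could push the share higher. These figures illustrate sensitivity and are not estimates for this trial.

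**At the Week 24 lock.** For a participant with only the Week 12 and Week 24 samples, the nominal labels are + + Transient, + − Transient and − + Indeterminate. None of these three patterns is persistent; under ≥78 days, + + would be.

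This applies to later-enrolled participants. When the last participant reaches Week 24, anyone randomized at least 36 − 24 = 12 weeks earlier has reached the Week 36 target. SAP version 4.0 is dated 11 November 2021, and Protocol 9.4 requires the SAP to be final before the lock. Counting back 252 days (Day 253 less Day 1) from that date gives 4 March 2021, so participants randomized by then had reached their Week 36 target. The withdrawn Amendment 02 used a 22 March 2021 cut-off so that at least 135 participants could reach Week 24. As a rough timing guide only, that date plus 252 days is 29 November 2021. The lock date itself is not given.

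**Alternative repairs.**

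- ≥84 days on actual dates: 21 + 7 = 28 of 49 offset pairs qualify, so timing still decides.
- ≥84 days on nominal visits: the Table 13 Week 24 ADA window is Days 127 to 210, so an early end-of-treatment sample on Day 130 counts as Week 24. Positives on Days 85 and 130, 45 days apart, would be called persistent.
- ≥78 days on actual dates: 49 of 49 in-window pairs qualify.

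**The case against.** The strongest defence is that the rule is a deliberately strict standard, meant to be met by three positives. Actual dates are also the more natural reading: the threshold is in days, Protocol 8.5.1.1 has collection dates recorded, and Table 13 serves by-visit summaries. On that reading adjacent positives can qualify, and what remains is ordinary sensitivity at a cut-off. Any lower cut-off only moves the boundary.

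Part of this stands. Actual dates are the better basis, and every threshold has an edge. But a cut-off in the middle of the permitted range of gaps differs from one at its end: the first splits compliant participants, the second does not. The strict-standard reading also fits poorly with a definition that admits two positives, and on actual dates it would not be enforced, since 21 of 49 compliant offset pairs pass.

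Three stronger inferences are tempting and are not supported.

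- **That the persistent class is empty.** Three consecutive positives qualify on the first-to-last reading, as do positives at Weeks 12 and 36 with Week 24 missing.
- **That the CSR cannot report persistent cases because of the Week 24 lock.** The available dates suggest that many participants would have a Week 36 sample by then, and SAP 4.9 adds later data through the update and addendum. Early discontinuers can also have extra samples (Protocol 1.3, footnote b): positives on Days 40, 85 and 169 span 129 days without Week 36. The addendum does not, however, repair the rule.
- **That the immunogenicity endpoint or efficacy conclusions are affected.** Treatment-emergent ADA incidence, the ADA-positive and ADA-negative groups and the efficacy tests do not use persistence.

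**Conclusion.** The point holds and is minor. The arithmetic rests only on the documents: on nominal days two adjacent scheduled positives never qualify as persistent; on actual dates the gap runs from 78 to 90 days and permitted visit timing decides the label. Later-enrolled participants without a Week 36 sample at the lock are the most exposed in the CSR.

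The effect is confined to the descriptive persistent and transient counts, titers by class and associations that the SAP says may be explored. The concentration plot by ADA classification could be touched if it uses these classes.

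The number of participants affected cannot be computed. The documents give no expected ADA rate, visit-offset distribution or lock date, and China sites collect no scheduled ADA samples (Protocol 10.10). The statement that the class is not empty assumes the first-to-last reading, which the SAP should make explicit.

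**What to change.** In SAP 4.8.2, state that separation is measured on actual sampling dates, from the first to the last positive sample in an unbroken run of positives, and that the 12-week criterion carries the protocol's visit-window tolerance: 84 − 6 = 78, so at least 78 days. Leave Indeterminate and Transient as defined. Every in-window pair of adjacent scheduled positives is then classified the same way.

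The cost is one sentence and no new data. The persistent count may rise, possibly materially, and the transient count falls by the same number. Some cases stay Transient: out-of-window pairs under 78 days (Days 89 and 166 are 77 days apart) and short runs that end in an early end-of-treatment sample, even where no later sample exists. For comparison with analyses that use the more-than-84-day rule, add a footnote or a side-by-side count under that rule.
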